The key secondary endpoint is the percentage of subjects abstinent during Weeks 22 through 25 on the mITT population. The analysis will be performed using a fully covaried logistic regression that includes treatment group, clinical site, pre-randomization drinking goal (abstinence versus not abstinent), and baseline percent days abstinent as covariates; however, fewer covariates may be included given a limited number of observed events. Subjects with any missing drinking data during Weeks 22 to 25 will be considered non-abstinent. Statistical significance will be evaluated if and only if the primary endpoint (PSNHDD) is statistically significant (p<0.05). The testing procedure utilizes serial gate keeping methodology (Dmitrienko and Tamhane 2009). If statistical significance for the primary endpoint of PSNHDD is met then the Wald statistic from the fully covaried logistic regression will be used to test treatment differences in the percentage of subjects abstinent with statistical significance identified with a two-tailed p-value below 0.05.

Analysis of the Supportive Secondary Endpoints:

Secondary endpoints will compare the HORIZANT Extended-Release Tablets group with the placebo group using mixed-effects models. Covariates for continuous secondary efficacy endpoints include the baseline equivalent of the endpoint, clinical site, treatment, time and the treatment by time interaction. Additional covariates for the secondary efficacy endpoints may include baseline characteristics with a theoretical and/or empirical basis for a relationship with a particular secondary endpoint. In general, every continuous secondary efficacy endpoint is analyzed using a repeated measures mixed effects model where subjects are random effects; factors and covariates are fixed effects. The overall least squares means and least square means for each time point along with the 95% confidence intervals will be presented for the untransformed endpoint only, while two-tailed p-values and Cohen's d will be presented for both the untransformed and transformed data. Inference and Cohen's d will be based upon the results using

appropriately transformed data. Percent subjects with a WHO 1-level decrease in alcohol consumption and a WHO 2-level decrease in alcohol consumption will be analyzed via a fully covaried logistic regression of the endpoint measured during the last 4 weeks of the maintenance period. No imputation will be used for the analysis of secondary endpoints.

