11.11. Drinking Question

If a subject is withdrawn from the study early and is no longer participating in clinic visits or providing TLFB drinking data but is willing to be contacted by phone at the week most proximal to dropout, then they will be asked about any drinking and heavy drinking during the time since last contact. Phone calls will continue until the end of the treatment period, as deemed acceptable by the patient, to obtain data on the primary efficacy endpoint (any heavy drinking days defined as 5 drinks per day for males and 4 drinks per day for females) and on the secondary efficacy

endpoint of abstinence. The rules regarding standard drinking units (SDU) applies. This data will be recorded on a source document and eCRF. This does not apply to subjects who are willing to supply daily drinking data by the TLFB method.

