11.33. TLFB Interview

Drinking behavior will be assessed using the TLFB methodology (Sobell & Sobell-1992). The TLFB is a semi-structured interview that provides estimates of the daily quantity of alcohol consumption during specified time periods. It uses a calendar prompt and a number of other memory aids (e.g., holidays, payday, and other personally relevant dates) to facilitate accurate recall of drinking or other drug use during the target period. The procedure has been widely used in clinical and research contexts. It has demonstrated adequate levels of reliability and validity when administered as an in-person interview, over the telephone, and when administered via computer (Carey-1997, Sobell et al-1988, Sobell et al-1996). After consent is signed, the TLFB interview will be performed for the 28-day period prior to signing consent. Thereafter, the interview will be for the previous days between the last assessment and the day prior to the day of the assessment. It is estimated that a 28-day TLFB assessment will take 20 minutes to complete. In the event of missed visits, collection of missed drinking data at the following visit is required.

If a subject requests to withdraw from the study but agrees to continued telephone contact to assess drinking, the TLFB will be performed over the phone for the duration of the study at a frequency acceptable to the study subject and site staff.

An Excel spreadsheet customized for use in this study will be used for double data entry by clinical site staff to collect the TLFB drinking data. This spreadsheet contains a calculator to

determine standard drink units (SDUs). This spreadsheet will be reviewed, compared with source documents and collected by study monitors for upload into the main study database.

Drinking days are defined as the number of days in which the subject reported any alcohol consumption (i.e., > 0 standard drinking units [SDUs]). A standard drink contains approximately 0.6 fluid ounces (oz) of pure alcohol. The data given by the subjects on amount and type of alcoholic beverage(s) consumed will be converted to SDUs. Standard drink unit definitions are provided in Table 8.

Table 8: Standard Drink Unit Definitions

For Beer ($\sim 5\%$ alcohol), the approximate number of SDUs in:

- 12 oz = 1.0
- 16 oz = 1.3
- 22 oz = 2.0
- 40 oz = 3.3

For malt liquor (~ 7% alcohol), the approximate number of SDUs in:

- 12 oz = 1.4
- 16 oz = 1.9
- 22 oz = 2.6
- 40 oz = 4.7

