12.4.2. Analysis Addressing the Primary Efficacy Endpoint

The primary analysis will be conducted via a fully covaried logistic regression analysis of the PSNHDD during Study Weeks 22 to 25 (last 4 weeks of the maintenance period on the mITT population). The model includes treatment group, clinical site, pre-randomization drinking goal (abstinence versus not abstinent), and baseline percent heavy drinking days (in the 28-day period prior to the date that the subject signed the informed consent form). Exploratory analyses will examine other timeframes beyond the last 4 weeks. A two-tailed p-value < 0.05 will be considered statistically significant. The primary analysis will use all mITT subjects and will employ imputation for missing drinking data such that any subject with any missing drinking data during the evaluation period for this endpoint will be imputed as a subject with a heavy drinking day.

Prior to the subject dropping out of the study, every attempt will be made to continue to collect TLFB data; however, if the subject does not want to participate in the collection of the TLFB they will be asked to participate in a periodic follow-up phone call to collect a summary of drinking information. If the subject agrees to be contacted then they will be asked about any drinking and heavy drinking during the time since last contact. Phone calls will continue until the end of the treatment period, as deemed acceptable by the patient. The two questions cover whether the subject had any heavy drinking days or drinking days during the period covered. This summary drinking data will be used for the primary endpoint when TLFB data are not available. If the subject does not agree to participate with phone contact, thus no summary drinking data nor TLFB data is available, then imputation as indicated above will be used. An

analysis of PSNHDD without imputation for missing data will be performed as an exploratory analysis.

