12.4.3. Secondary Efficacy Endpoints Analysis

12.4.3.1. Key Secondary Endpoint: Percentage of Subjects Abstinent from Alcohol

Percentage of subjects abstinent during Weeks 22 to 25 is the key secondary endpoint. Covariates for percentage of subjects abstinent will be the same as those for the primary endpoint PSNHDD as described in Section 9.4.2. Fewer covariates for the logistic regression may be used depending upon the number of events. If the number of events permits the inclusion of a baseline drinking covariate, the percentage of days abstinent will be used as the covariate for the percent subjects abstinent endpoint. The testing procedure utilizes the serial gate keeping methodology (Dmitrienko and Tamhane-2009). The key secondary endpoint can only be evaluated for statistical significance after the primary endpoint has been identified as statistically significant. In this situation, percentage of subjects abstinent will be evaluated using the Wald statistic from the logistic regression model at p<0.05 after PSNHDD is found to have p<0.05. If PSNHDD is not statistically significant at the 0.05 level then no significance testing of percentage of subjects abstinent will be performed. This analysis will be performed on mITT subjects with no imputation for missing data. However, if drinking data are missing by TLFB, but the subject reports any drinking during Weeks 22 to 25 using the Drinking Question eCRF, then the subject will be considered not abstinent. An analysis of percent subjects abstinent without imputation for missing data will be performed as an exploratory analysis.

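### For the gate-kept abstinence endpoint, the Drinking Question has a stated effect only when drinking is reported; a subject giving only that question and reporting none has no written route to being a responder

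*Protocol*

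**What the plan says.** All references are to the protocol.

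- **Section 11.11 (Drinking Question).** Subjects who have left the study early, no longer give TLFB data and accept calls are contacted by telephone; "then they will be asked about any drinking and heavy drinking during the time since last contact". The section gives both the primary endpoint and abstinence as the reason for the calls. It exempts subjects willing to give TLFB.
- **Section 12.4.2 (primary endpoint).** "The two questions cover whether the subject had any heavy drinking days or drinking days during the period covered". The use is not limited to one answer: "This summary drinking data will be used for the primary endpoint when TLFB data are not available". Only when neither source exists is the subject imputed as having a heavy drinking day.
- **Section 12.4.3.1 (abstinence, key secondary).** "This analysis will be performed on mITT subjects with no imputation for missing data". The one exception, for missing TLFB data, is: "but the subject reports any drinking during Weeks 22 to 25 using the Drinking Question eCRF, then the subject will be considered not abstinent".
- **Synopsis, Analysis of the Key Secondary Endpoint.** "Subjects with any missing drinking data during Weeks 22 to 25 will be considered non-abstinent". The Drinking Question is not mentioned for this endpoint.
- **Section 11.33 (TLFB Interview).** For a subject who withdraws but accepts telephone contact, "the TLFB will be performed over the phone for the duration of the study".
- **Section 12.4.11.** Abstinence is tested at the full two-sided 0.05 if the primary endpoint is significant.

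**The concern.** The protocol collects a two-way answer for two endpoints. It uses the answer without limit of direction for the primary endpoint, and states a use for only one direction for abstinence. The same call can make a subject a responder on the primary endpoint and leave that subject excluded, or a failure, on abstinence.

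Under the no-imputation wording, whether a telephone-only subject enters the analysis depends on the outcome: those who drank go into the denominator and those who did not stay out. That is selection on the outcome in the only secondary endpoint with a confirmatory test. Events may also be few; both the synopsis and Section 12.4.3.1 allow covariates to be removed for that reason. Two analysts could reasonably classify the same subject differently.

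**Working it through.** **Step 1. Classification as written.** Take a withdrawn subject with no TLFB for Weeks 22 to 25 who answers only the Drinking Question.

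| Answer | Primary endpoint (12.4.2) | Abstinence, 12.4.3.1 | Abstinence, synopsis |
|---|---|---|---|
| Heavy drinking | non-responder | not abstinent, included | not abstinent |
| Drinking, none heavy | responder | not abstinent, included | not abstinent |
| No drinking | responder | no rule; missing, so excluded | missing, so not abstinent |

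The last row has no route to abstinence responder under either text.

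**Step 2. The plan's own figures.** None is given for abstinence. The stated 91% power for the primary endpoint (173 per group, 13% v 27%) reproduces at 90.6% with pooled variance and 91.0% with the arcsine method. It is not affected. From Section 12.5 I take 173 per group and 15% dropout: 0.15 × 173 = 25.95, about 26, leaving 147.

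**Step 3. Effect on one arm under 12.4.3.1.** Let c be the share with TLFB, p the telephone-only share and r the true abstinence rate, assumed the same in both sources.

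- Observed rate = c·r / (c + p(1 − r)).
- Observed odds = c·r / ((c + p)(1 − r)), which is the true odds multiplied by c/(c + p).

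With c = 0.85, p = 0.10, r = 0.15 (p and r assumed): 0.1275 / (0.85 + 0.085) = 13.6% instead of 15%. If both arms have these shares, both read 13.6%.

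**Step 4. True difference, equal shares.** Assumptions: abstinence of 4.1% v 17.0%, borrowed from the earlier 12-week gabapentin trial in Section 4.3.7 (placebo and 1800 mg); 25% to 100% of the 26 dropouts answer; their abstinence is equal to, or half of, that of the 147.

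- Example, all 26 answer at the same rates. Active: 147 × 0.17 = 24.99 responders; denominator 147 + 26 × 0.83 = 168.58; 14.8%. Placebo: 6.03 / (147 + 26 × 0.959) = 6.03 / 171.93 = 3.5%. The difference is 11.3 points, against 12.9 with both answers used.
- Over the whole range, 12.4.3.1 as written gives 3.5–3.9% v 14.6–16.4%; using both answers gives 3.8–4.1% v 15.7–17.0%. The two-way rule adds 0.1–1.1 placebo and 0.6–4.4 active responders.
- Synopsis rule: 3.5% v 14.5% as written; 3.6–4.1% v 14.8–17.0% if the answer of no drinking is counted first.

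On the odds-ratio scale, which the planned logistic regression estimates, equal shares cancel: c/(c + p) multiplies the odds in both arms. In the example the odds ratio is 4.79 either way, and the cost is precision. The standard error of the log odds ratio is √(1/6.03 + 1/165.91 + 1/24.99 + 1/143.59) = 0.468 as written, against √(1/7.09 + 1/165.91 + 1/29.41 + 1/143.59) = 0.434 with both answers.

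**Step 5. Unequal shares, no true effect, r = 0.15.** Keep 85% TLFB in each arm, in line with the planned dropout.

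- p = 0.05: 0.1275 / (0.85 + 0.0425) = 14.3%.
- p = 0.10: 13.6%, as above. The gap between p = 0.05 and p = 0.10 is about 0.7 points.
- Extremes, p = 0 v p = 0.15: 15.0% v 0.1275 / 0.9775 = 13.0%, a gap of 2.0 points (odds ratio 0.85, or 1/0.85 = 1.18 the other way).

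For scale, the standard error of a difference at 15% with 173 per arm is √(2 × 0.15 × 0.85 / 173) = 3.8 points.

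**The case against.** **Telephone TLFB.** A reader might infer that no telephone report can make a withdrawn subject abstinent. Section 11.33 rules that out: full TLFB can be taken by telephone, and such a subject with no drinking in Weeks 22 to 25 is a responder. The point is confined to those who refuse TLFB in every form but answer the Drinking Question, and that group may be small.

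**Silence is not prohibition.** A reader might also infer that the protocol discards an answer of no drinking. It does not say so. Section 11.11 suggests the answer was meant to count, and one can argue that a subject who gave it has drinking data and is not missing. This stands as a plausible reading of intent. It does not settle the matter, because Section 12.4.3.1 treats the answer as an exception for missing TLFB and spells out one half only. Followed literally, that half selects on outcome.

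**Some asymmetry is logical.** One report of drinking disproves abstinence whatever period it covers; a report of no drinking proves it only if every missing day is covered, and calls continue only as the subject accepts. This is right and calls for a coverage condition. It does not justify leaving the answer undefined.

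**Bias between arms.** A reader might conclude that the rule distorts the treatment comparison. The documents give no reason to expect unequal telephone-only follow-up; Section 12.5 plans 15% dropout in each group. With equal shares there is no spurious difference.

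**A larger defect next to it.** Outcome-dependent inclusion arises only under the no-imputation wording. The synopsis says the opposite, and Section 12.4.3.1 itself lists a non-imputed analysis as exploratory, as if the main one were imputed. That stands, and both should be settled together.

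**Conclusion.** The point holds for withdrawn subjects who give only the Drinking Question. An answer of no drinking has no written route to an abstinence success under either missing-data rule, although it is collected for that purpose and accepted for the primary endpoint.

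The effect is modest. Under Section 12.4.3.1 the observed rate falls in each arm, by up to about 0.6 points on placebo and 2.2 on active in the illustration. With equal shares a true difference shrinks by about 0.2 to 1.6 points, while the odds ratio is essentially unchanged and precision is lost. A false difference needs unequal telephone-only shares; within 15% dropout and at 15% abstinence it cannot exceed about 2 points. All of this rests on assumed response and abstinence rates, and on telephone-only abstinence equal to, or half of, that of the other subjects. The protocol supplies none of these for this endpoint. The case for action is that a confirmatory classification rule is half written, more than the likely size of the bias.

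**What to change.** In Section 12.4.3.1, and in the same words in the synopsis, state that when TLFB data are missing for any part of Weeks 22 to 25 the Drinking Question is used in both directions:

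- any drinking reported in Weeks 22 to 25: not abstinent;
- no drinking reported, with answers covering every day of Weeks 22 to 25 that TLFB does not cover, and no drinking on the TLFB days: abstinent.

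Apply this before the missing-data rule, and choose one missing-data rule so that the synopsis and Section 12.4.3.1 agree. Carry the wording into the SAP before unblinding.

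The cost is a short text change; the answers are already collected, though the period each call covers must be recoverable from the eCRF. The downside is that a few abstinence successes will rest on a summary telephone report, which the primary endpoint already accepts.

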12.4.3.2. Supportive Secondary Efficacy Endpoints

Supportive secondary efficacy endpoints will also be analyzed based on data during the last 4 weeks of the maintenance period (Weeks 22 through 25), including TLFB and other questionnaire data assessed at Week 26 that reflect data collected during this period. No imputation will be done on any supportive secondary efficacy endpoint.

In general, every continuous secondary efficacy endpoint is analyzed using a repeated measures mixed effects model where subjects are random effects; factors and covariates are fixed effects.

The primary analysis model for all continuous endpoint is:

• Appropriately transformed endpoint = treatment + week + treatment*week + clinical site + baseline equivalent of endpoint + covariates

Covariates for continuous secondary efficacy endpoints include the baseline equivalent of the endpoint, clinical site, treatment, time and the treatment by time interaction. Additional covariates for the secondary efficacy endpoints may include baseline characteristics with a theoretical and/or empirical basis for a relationship with a particular secondary endpoint.

Such characteristics may include, but are not limited to, drinking goal (total abstinence versus less than total abstinence), age, years of regular drinking (age minus age first started drinking alcohol regularly), baseline alcohol craving scale total score. Prior to the unblinding of the data, matrices of correlations between these baseline characteristics and each of the secondary efficacy endpoints, pooled across blinded treatment assignment, will be produced (using Pearson for continuous variables, Spearman for categorical outcomes). Selection of baseline variables to

include as covariates in the models will be based on consideration of the following criteria: at least modest correlation with outcome (i.e., $r \ge 0.20$), and clinical expertise. Each endpoint may have a unique set of covariates. Care is taken to only select a limited number of covariates such that the models are not over fitted.

This primary model will also be applied to the untransformed endpoint.

Results based on the primary analysis model and the model of the untransformed endpoint will be presented in tabular form. The overall least squares means and least square means for each time point along with the 95% confidence intervals will be presented for the untransformed endpoint only, while two-tailed p-values and Cohen's d will be presented for both the untransformed and transformed data. Inference and Cohen's d will be based upon the results using appropriately transformed data.

Analysis of the dichotomous secondary drinking endpoints, percent subjects with a WHO 1- and 2-level decrease in alcohol consumption (Aubin et al-2015), will be conducted via a fully covaried logistic regression model and contingency table. Covariates for the logistic regression model will be selected using a similar approach as that used for the primary endpoint PSNHDD as described in Section 9.4.2. Fewer covariates for the logistic regression may be used depending upon the number of observed events. No baseline drinking covariate will be employed for the endpoints, as these endpoints already adjust for baseline drinking in their calculation.

Covariates for both of these endpoints will be pre-specified in the SAP.

Analyses of supportive secondary endpoints with imputation for missing data will be performed as exploratory analyses.

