8.3. Selection and Withdrawal of Subjects

8.3.1. Inclusion Criteria

Subjects must meet each one of the following inclusion criteria in order to be eligible for participation in the study:

- 1. Be at least 21 years of age.
- 2. Have a current (past 12 months) DSM-5 diagnosis of AUD (4 or more symptoms) assessed using the MINI neuropsychiatric interview version 7 (moderate severity, ICD-10-CM Code F10.20 alcohol dependence, uncomplicated).
- 3. If male, report drinking an average of at least 28 drinks per week or if female report drinking an average of at least 21 drinks per week for the 28-day period prior to consent and for both males and females one heavy drinking day per week over the 28-day period.
- 4. Have a BAC by breathalyzer equal to 0.000 when s/he signed the informed consent document (either just prior to or immediately after signing consent).
- 5. Be abstinent (by self report) in the 3-days prior to the day of randomization and have a BAC of 0.000 by alcohol breathalyzer on the day of randomization.

- otocoi Number: NCIG-006
 - 6. Be seeking treatment for problems with alcohol.
 - 7. Be able to verbalize an understanding of the consent form, able to provide written informed consent, verbalize willingness to complete study procedures, able to understand written and oral instructions in English and able to complete the questionnaires required by the protocol.
 - 8. Agree (if the subject is female and of child bearing potential) to use at least one of the following methods of birth control, unless she is surgically sterile, partner is surgically sterile or she is postmenopausal:
 - a. oral contraceptives,
 - b. contraceptive sponge,
 - c. patch,
 - d. double barrier (diaphragm/spermicidal or condom/spermicidal),
 - e. intrauterine contraceptive system,
 - f. etonogestrel implant,
 - g. medroxyprogesterone acetate contraceptive injection,
 - h. complete abstinence from sexual intercourse, and/or
 - i. hormonal vaginal contraceptive ring.
 - 9. Be able to take oral medication and be willing to adhere to the medication regimen.
 - 10. Complete all assessments required at screening and baseline.
 - 11. Have a place to live in the 2 weeks prior to randomization and not be at risk that s/he will lose his/her housing by Study Week 28.
 - 12. Not anticipate any significant problems with transportation arrangements or available time to travel to the study site by Study Week 28.

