11.34. World Health Organization Drinking Risk Categorical Scale

The WHO has developed a drinking risk categorical scale that can be used in a responder analysis approach to assess clinically relevant decreases in alcohol consumption (Aubin et al-2015). Two dichotomous endpoints will be analyzed: WHO 1-level and WHO 2-level decrease in alcohol consumption. The WHO 1- and 2-level decrease endpoints are the percentage of subjects experiencing at least 1- and 2-level decrease in WHO levels of alcohol consumption, respectively, from the level at baseline (the period including the 28 days before screening) to the level during the last 4 weeks of the maintenance phase (Study Weeks 22-25).

The WHO levels of average alcohol consumption per day are as follows:

	Males	Females
Low Risk	1 to 40g	1 to 20g
Medium Risk	41 to 60g	21 to 40g
High Risk	61 to 100g	41 to 60g
Very High Risk	101+g	61+g

where 14g = 1 SDU (WHO-2000). In computing the WHO alcohol consumption level, average drinks per day will be used, computed as the sum of all drinks in the 28 day period divided by the number of days with non-missing drinking data in that period. Abstinent subjects will be included in a separate "Abstinent" category. A subject must have at least 1 week of data during the last 4 weeks of the maintenance phase to be considered non-missing.

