12.4.11. Multiple Comparison/Multiplicity

The primary endpoint and key secondary endpoint use the serial gate keeping methodology (Dmitrienko and Tamhane 2009) to maintain a family-wise Type I error of 0.05. This process requires an ordering of the hypotheses; namely, that the primary hypothesis for PSNHDD is evaluated first, followed conditionally by the key secondary hypothesis for percentage of subjects abstinent. This procedure requires that the primary hypothesis be rejected at p<0.05 then the hypothesis for the key secondary endpoint may be evaluated. If the primary hypothesis is not rejected then there is no test for the key secondary hypothesis. The serial gate keeping methodology indicates that if the primary hypothesis is rejected then the entire alpha (0.05, two-

sided) is available for the key secondary hypothesis. As such, the key secondary endpoint of percentage of subjects abstinent is evaluated at p<0.05 (two-sided) for statistical significance.

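### The protocol bars a baseline drinking covariate from the WHO 1- and 2-level models for an incorrect reason; the bar causes no bias but may give up a little power

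*Protocol*

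**What the plan says.** Section 11.34 defines the endpoints: "The WHO 1- and 2-level decrease endpoints are the percentage of subjects experiencing at least 1- and 2-level decrease in WHO levels", measured from baseline to Study Weeks 22-25. The bands are in grams per day at 14 g per standard drink. For men the upper limits of Low, Medium and High are 40, 60 and 100 g; for women they are 20, 40 and 60 g. Abstinence is kept apart: "Abstinent subjects will be included in a separate" category.

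Section 12.4.3.2 analyses both endpoints by logistic regression. On covariates it says "Covariates for the logistic regression model will be selected using a similar approach as that used for the primary endpoint PSNHDD" (its cross-reference reads 9.4.2, but the description stands at 12.4.2). It adds "Fewer covariates for the logistic regression may be used depending upon the number of observed events", and then the disputed rule: "No baseline drinking covariate will be employed for the endpoints, as these endpoints already adjust for baseline drinking in their calculation". The remaining covariates are left to the SAP.

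The primary model in section 12.4.2 does carry a baseline drinking term: "The model includes treatment group, clinical site, pre-randomization drinking goal (abstinence versus not abstinent), and baseline percent heavy drinking days". Section 12.4.3.1 uses baseline percentage of days abstinent for the key secondary endpoint if events permit, and section 12.4.3.2 puts the baseline equivalent into every continuous secondary model.

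**The concern.** Subtracting a baseline category from a follow-up category does not make the result independent of baseline. Band widths differ, the entry criteria cut off the lower end, and the scale has a floor, so subjects who cut their drinking by the same percentage can differ in response only because of where they started. If so, the reason given for excluding the term fails, and a prognostic variable the trial already holds is barred however many events occur.

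What is at stake is limited: some power, and adjustment for chance imbalance in baseline drinking, since randomisation is stratified by site only (section 8.6.1). Both endpoints are supportive and outside the formal testing sequence, which covers only two others: "The primary endpoint and key secondary endpoint use the serial gate keeping methodology".

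**Working it through.** **The plan's own figure.** The protocol gives no rates or power for the WHO endpoints. Its one calculation is for the primary endpoint: 13% against 27%, 173 per group, 91% power. Check: z = [0.14 × √173 − 1.96 × √(2 × 0.20 × 0.80)] / √(0.13 × 0.87 + 0.27 × 0.73) = (1.841 − 1.109) / 0.557 = 1.316, so power is 90.6%. The figure reproduces. It is used here only for the number analysed: with 15% dropout and no imputation for the WHO endpoints, 346 × 0.85 = 294.

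**Step 1: where eligible subjects start.** Section 8.3.1 sets the floors as weekly counts of drinks: "If male, report drinking an average of at least 28 drinks per week or if female report drinking an average of at least 21". In grams per day:
- Men: 28/7 × 14 = 56 g, inside Medium (41 to 60 g).
- Women: 21/7 × 14 = 42 g, inside High (41 to 60 g), so no eligible woman starts at Medium.

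**Step 2: the cut needed to respond.** Required cut = 1 − (upper limit of target band) / (baseline grams). Abstinent is taken as the level below Low. Section 11.34 does not rank it; if it did not count as a level, a man at Medium could not fall two levels at all.

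| Men, baseline g/day | Level | Cut for 1 level | Cut for 2 levels |
|---|---|---|---|
| 56 | Medium | 1 − 40/56 = 29% | abstinence |
| 61 | High | 1 − 60/61 = 2% | 1 − 40/61 = 34% |
| 100 | High | 1 − 60/100 = 40% | 1 − 40/100 = 60% |
| 101 | Very High | 1 − 100/101 = 1% | 1 − 60/101 = 41% |
| 200 | Very High | 1 − 100/200 = 50% | 1 − 60/200 = 70% |

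For women the 2-level cut is 1 − 20/42 = 52% at 42 g, 1 − 40/61 = 34% at 61 g and 1 − 40/120 = 67% at 120 g. Apart from the rank of Abstinent, this step needs no assumption.

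**Step 3: what that does to response.** Suppose every subject has the same distribution of percentage cut (assumed: 12% abstinent, otherwise median cut 50%, log-SD 0.7). Then P = 0.12 + 0.88 × Φ[(ln(limit/baseline) − ln 0.5)/0.7].

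| Men, g/day | P(1-level) | P(2-level) |
|---|---|---|
| 58 | 71.6% | 12.0% |
| 61 | 85.3% | 69.3% |
| 100 | 65.0% | 45.0% |
| 101 | 85.5% | 64.6% |
| 200 | 56.0% | 32.5% |

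An identical distribution of percentage cuts gives quite different response rates by starting level. The calculation has not removed baseline.

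**Step 4: power, by simulation.** All distributional inputs are assumptions. There were 1,500 trials per row with n = 294 and 65% men. Baseline was log-normal (medians 130 g men, 95 g women; log-SD 0.5), truncated at the entry floors. Placebo abstinence was 10%, plus 4 points on drug, with an extra log reduction on drug of 0.25 to 0.3. The logistic Wald test had treatment and 10 sites in the model, without and with log baseline drinking standardised within sex. The log-log slope of follow-up on baseline is correlation × follow-up log-SD / 0.5.

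| Correlation, log-SD | Slope | 1-level power without → with | 2-level power without → with |
|---|---|---|---|
| 0.2, 0.8 | 0.32 | 64.5 → 64.8% | 71.7 → 71.7% |
| 0.4, 0.8 | 0.64 | 63.0 → 63.7% | 73.9 → 74.0% |
| 0.4, 0.8 (smaller overall drop) | 0.64 | 76.3 → 77.3% | 77.2 → 77.2% |
| 0.6, 0.6 | 0.72 | 77.1 → 79.6% | 87.9 → 89.8% |
| 0.75, 0.6 | 0.90 | 86.5 → 92.5% | 90.7 → 92.1% |
| 0.6, 0.8 | 0.96 | 69.9 → 74.9% | 79.3 → 82.2% |

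Gains run from 0.3 to 6.0 points (1-level) and 0 to 2.9 points (2-level), and are smallest where the slope is low. With no treatment effect (correlation 0.6), rejection was 4.7% without and 5.3% with the term (1-level), and 4.4% and 4.9% (2-level). The Monte Carlo standard error is about √(0.05 × 0.95/1500) = 0.6 points.

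A second set of 12 scenarios had follow-up proportional to baseline (slope 1) and used log drinks with sex. It gave +0.8 to +5.9 points for the 1-level endpoint. Efficiency changed by −0.2% to +8.9% for the 2-level endpoint.

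**The case against.** **The comparison is valid as planned.** A reader might infer from the wrong rationale that the WHO results would be biased or their p-values unreliable. The documents do not support that: treatment is randomised, and null rejection was about 5% either way. Nor does adding the term shrink the standard error of the log odds ratio. In the proportional scenarios it rose slightly (by 0.006 to 0.028 for the 1-level endpoint). The adjusted odds ratio is conditional, a different estimand and not a corrected one. This stands.

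**The power loss is not established.** A reader might take the upper end of the range as what the trial loses. That end depends on follow-up drinking staying nearly proportional to baseline, although entry selects on high recent drinking and regression to the mean is plausible. At log-log slopes of 0.3 to 0.5, efficiency gains were about 0 to 1.4% (1-level) and 0 to 1% (2-level), against about 5 to 7% for the 1-level endpoint at slope 1. This also stands, and is why the claim is that power may be lost.

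**Overfitting.** Section 12.4.3.2 warns against it, but the allowance for fewer covariates when events are few already covers that risk. It does not justify an unconditional bar. Adding the WHO level as a factor would create a sparse Medium cell, so a continuous term is preferable.

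**Covered elsewhere.** The continuous consumption endpoints are baseline-adjusted, and section 12.1 lets the SAP amend the proposed analyses. That lowers the stakes. The bar and its reason are nevertheless fixed in the protocol, so this is not a detail left to the SAP.

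**Conclusion.** The stated reason is incorrect on the protocol's own bands and entry criteria, and that conclusion needs no distributional assumption. The consequence is minor: no bias, no type I error inflation, chance baseline imbalance left unadjusted, and a possible power loss of roughly 0 to 6 points (1-level) and 0 to 3 points (2-level) on two supportive endpoints. Those ranges rest on assumed distributions, because the protocol gives none for baseline or follow-up drinking, and the loss may be nil. The text is not strictly self-contradictory either: the bar is an explicit exception to the primary-endpoint approach, but one whose reason fails.

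**What to change.** Delete the sentence in section 12.4.3.2. Prespecify in the SAP, before unblinding, one baseline drinking term for both WHO models: log mean drinks per day over the 28-day baseline, with sex because the bands differ by sex. Keep it subject to the existing allowance for fewer covariates when events are few; the other covariates stay as the SAP specifies. No WHO-level factor and no rule for merging levels is needed.

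The cost is one or two model degrees of freedom and no new data, since baseline drinking is already computed to assign the baseline level. The reported odds ratio becomes conditional on baseline drinking, and there may be no gain.
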